In this study, we aim to test whether a provider-level educational intervention in the form of targeted, practical, action-oriented education to primary care physicians and nurses on safety and effectiveness of and how to use evidence-based smoking cessation treatment for those with psychiatric illness, termed academic detailing (AD), alone or in combination with practical support offered to the primary care physician / primary care team and the smoker with SMI in the form of a community health worker (CHW) will improve recommendation and utilization of standard of care smoking cessation treatments to and by those with SMI and, if so, whether the intervention improves smoking cessation rates for adults with SMI who smoke.

In addition, we aim to systematically identify and define barriers and facilitators to implementation of components of the integrated care intervention in primary care clinical settings using an interactive convergent mixed-methods design.

To do so, we will randomize primary care clinics that serve 3 or more, out of the approximately 1300 adult smokers with SMI who receive psychiatric rehabilitation services, Community Based Flexible Support (CBFS) or Assertive Community Treatment (ACT)), from the two largest providers of these services in the Boston area to either receive AD for their prescribers or not in a cluster randomized design. Half of the smokers with SMI in the study who receive primary care at the clinics assigned to the AD intervention to providers will be randomly assigned to be offered CHW support in addition to their ongoing psychiatric rehabilitation (CBFS or ACT) services. For participants who receive primary care from a clinic that serves two or fewer adult smokers with SMI, we will randomize half to receive CHW services and half to treatment as usual. See revised Schema below.

PCORI Large Pragmatic Trial: 1165 Adult Smokers with SMI Enrolled

II. SPECIFIC AIMS

In this cluster randomized study with embedded secondary randomization, comparing AD+CHW, AD, CHW and TAU, we seek to achieve the following aims:

Aim 1. Discover whether the AD+CHW intervention increases prescriber provision of advice and assistance to quit smoking and improves tobacco abstinence rates in smokers with SMI compared with usual care (TAU).

Hypothesis 1a. Smokers with SMI who receive AD+CHW will report higher rates of biochemically verified tobacco abstinence than those assigned to TAU at the Year 3 Assessment. This is the main outcome measure.

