
Exploratory hypotheses regarding effect of individual components of the intervention on abstinence rates:

Hypothesis 1b. Participants assigned to receive AD+CHW will demonstrate higher rates of biochemically-verified, 7-day point-prevalence tobacco abstinence than those assigned to AD at the Year 3 Assessment.

Hypothesis 1c. Participants assigned to receive AD will demonstrate higher rates of biochemically-verified, 7-day point-prevalence tobacco abstinence than those assigned to TAU at the Year 3 Assessment.

To include participants from Cohort 2, we include a secondary, factorial analysis using cohort as a factor, that was planned when we randomized participants whose clinics cared for ≤ 2 participants.

Hypothesis 1d. Participants assigned to receive CHW will demonstrate higher rates of biochemically-verified, 7-day point-prevalence tobacco abstinence than those assigned to TAU at the Year 3 Assessment.

Aim 2: Discover the effect of the AD+CHW interventions on patient-reported overall health, as measured by the SF-1, compared with TAU.

Hypothesis 2. Participants assigned to receive AD+CHW will report greater improvement in their overall health at their Year 3 Assessment compared to Baseline than those assigned to TAU.

Exploratory Aim 3: Evaluate feasibility of the AD+CHW intervention and assess factors that could impact implementation on a national scale.

Hypothesis 3. Identify differences in care processes between AD+CHW and TAU that may be suggestive of specific mechanisms.

Exploratory Aim 4: Evaluate subgroup differences in rates of biochemically-verified, 7-day point prevalence tobacco abstinence among participants diagnosed with schizophrenia and schizoaffective diagnoses compared to participants with other diagnoses.

Hypothesis 4a. Participants with schizophrenia and schizoaffective diagnoses will demonstrate lower absolute rates of biochemically-verified, 7-day point-prevalence tobacco abstinence compared to those with other diagnoses

Hypothesis 4b. Participants with schizophrenia and schizoaffective diagnoses will demonstrate a larger effect of treatment (AD+CHW) vs no treatment (TAU).

Aim 5: Systematically identify and define barriers and facilitators to implementation of components of the integrated care intervention in primary care clinical settings using an interactive convergent mixed-methods (qualitative and quantitative) design.

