As noted above, after enrollment was complete, but before the randomization, the protocol was amended because 13% (155 of 1165) of enrolled participants received primary care at 111 clinics that each served ≤ 2 enrolled participants. Because it was beyond the scope of the project to provide AD to so many clinics, prior to randomization, the decision was made and approved by the sponsor to include these 155 enrolled participants in a second cohort in a stratified randomization, such that Cohort 1 (AD-eligible) comprised participants seen in primary care clinics serving ≥ 3 enrolled participants described above. Cohort 2 (AD-ineligible) comprised participants whose primary care clinic served ≤ 2 enrolled participants who were randomized to CHW or TAU in a 1:1 ratio.

The patient population will consist of approximately 1300 adult outpatient smokers with SMI who receive psychiatric rehabilitation services through CBFS and ACT programs at Bay Cove Human Services and Vinfen Corporation. This includes adults primarily with schizophrenia spectrum disorders and bipolar disorder.

Inclusion/exclusion criteria:

Primary care clinics/physicians/nurses/care team: There are no requirements for clinics to be included or excluded except that they provide medical care to people with SMI who smoke and who are served by the CBFS and ACT psychiatric rehabilitation systems of Bay Cove and Vinfen. There are no exclusion criteria for prescribers related to specialty (e.g. internal medicine, psychiatry, pulmonary medicine, family medicine, clinical nurse specialist), experience with smoking cessation therapies, or experience working with people with SMI.

Since the patient and their prescriber will decide together on the timing of initiation of any pharmacotherapeutic cessation aid, there will be no exclusion criteria for patients due to medical illness or psychiatric symptom severity or stability or substance use.

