Only aggregate results across groups of providers or patients will be analyzed and shared; no information on individual providers or patients will be generated or shared. We will not publish or report any cell size with 10 or fewer participants in accordance with data suppression policies.

V. STUDY PROCEDURES

This study aims to compare the effects of service interventions, AD+CHW, AD, CHW and TAU, on smoking outcomes in a large community psychiatric rehabilitation system of care.

Allocation concealment: Intervention allocation will be randomly assigned by computer generated list.

Blinding: Neither participants nor providers will be blind to the intervention assigned. Research coordinators who conduct the surveys with all participants will be blind to intervention assignment to the extent possible as the participant may volunteer information that makes study assignment clear to the coordinator.

1. Overview of Survey Visits:

Research assistants will attend the annual, scheduled CBFS and ACT rehabilitation team treatment planning meeting in the community to conduct an annual survey when the psychiatric rehabilitation team is engaging with the patient. The schedule of psychiatric rehabilitation team meeting is fixed according to the month of enrollment in CBFS or ACT, and the study assessments will accommodate this schedule. The brief annual survey will take 5 minutes for most participants. Those who complete the baseline survey will be asked to repeat the survey at their next two annual psychiatric rehabilitation team meetings.

2. Survey Items

2.1 **Demographics:** age, sex, race, living situation (Group Home/Supervised Housing or Independent Living) (Baseline Assessment only)

2.2 **Smoking Status:** If smoking: number of cigarettes smoked per day; if prior smoker: time since last cigarette and quitting method.

2.3 **Smoking cessation services in the past year:** If smoking: report of whether smoking status was assessed by their primary care physician or nurse, whether advice to quit smoking was given, whether prescription of pharmacotherapeutic cessation aids and/or referral to behavioral smoking cessation treatment were offered or made.

- If pharmacotherapeutic cessation aids were prescribed, we will ask if the was filled, and, if so, whether the medication was used, and, if so, for how long.

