To include participants from Cohort 2, we conducted a secondary, factorial analysis of the impact of the two interventions and their combination, using cohort as a factor, that was planned when we randomized participants whose clinics cared for ≤ 2 participants.

To determine the influence of the assigned intervention mediated via its impact on TUD medication use, and varenicline use specifically, the unmediated impact of the study interventions on abstinence, and the impact of TUD medication use and varenicline use specifically on abstinence we conducted mediation analyses using the combined cohorts. We assessed associations between intervention assignment, TUD medication use, and year-2 abstinence via path analyses based on logistic regression. Separate analyses assessed the impact of taking any TUD medication and varenicline specifically. Estimates of the indirect effect were computed per each imputation run and pooled using Rubin's method.

2. Statistical methods.

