Aim 1. Hypothesis 1a. *Those who receive AD+CHW will demonstrate higher rates of biochemically verified tobacco abstinence than those who receive usual care (TAU).* The primary outcome will be the proportion of smokers who are abstinent at their Year Three Assessment. This will be 12-24 months after randomization to study interventions because assessments are conducted in the pragmatic setting of the annual psychiatric rehabilitation team meetings. This smoking abstinence rate will be compared between the two groups using a generalized linear mixed models logistic regression, with random effect for clinic, assumed to be normally distributed [114]. **Hypothesis 1b.** *Those who receive AD+CHW will demonstrate higher rates of biochemically verified tobacco abstinence than those who receive AD only.* This rate will be compared between the two groups using logistic regression. **Hypothesis 1c.** *Those who receive AD will demonstrate higher rates of biochemically verified tobacco abstinence than those received TAU.* This rate will be compared between the two groups using generalized linear mixed models logistic regression. Hypothesis 1d. Participants assigned to receive CHW will demonstrate a higher rates of biochemically verified, 7-day point-prevalence tobacco abstinence than those assigned to TAU at the Year 3 Assessment. This will be tested with factorial analysis in the combined sample, using cohort as a factor. Additionally, we will compare MassHealth pharmacy claims data for smoking cessation medications (varenicline, bupropion and nicotine replacement therapy) to examine differences in prescribing patterns of providers randomized to AD compared to those randomized to TAU. We will also examine the effect of the interventions on rates of participants filling prescriptions for smoking cessation medication (i.e. AD, AD+CHW, CHW, TAU)

Aim 2: Hypothesis 2. *Those who receive AD+CHW will demonstrate improved Quality of Life compared to those who receive usual care, as assessed with the SF-1 (Overall Health).* We will assess this hypothesis with a random effects model with baseline, duration of follow up, and treatment group as covariates and a clinic random effect. We will use data from the last visit during the study as the dependent measure.

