We are unsure of the effect the academic detailing (AD) intervention alone will have on abstinence rates. AD could inspire quit rates as low as 3-7%. Or AD may be nearly as effective as the combined effect of AD+CHW, with abstinence rates as high as 14-20%. Or the abstinence rates among those whose treaters receive AD without CHW support may lie somewhere in between, in the 9-10% range. Bearing these features in mind, we present the following tables with power estimations based on 1000 simulations, where T=TAU, A=AD and C=AD+CHW:

Table 1. Optimistic TAU, pessimistic AD + CHW, and a range of AD effects on abstinence rates:

TAU	AD	AD+CHW	ICC	T vs. A	T vs. C	A vs. C
.05	.07	.16	.03	.14	.96	.94
.05	.095	.16	.03	.51	.98	.67
.05	.14	.16	.03	.95	.99	.10

Table 2. Pessimistic TAU, optimistic AD+CHW, and a range of AD effects on abstinence rates:

TAU	AD	AD+CHW	ICC	T vs. A	T vs. C	A vs. C
.03	.07	.18	.03	.42	.99	.96
.03	.095	.18	.03	.88	.99	.87
.03	.14	.18	.03	.99	.99	.26

4. Sample Size Calculations

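### H1d (CHW vs TAU) is randomised only in Cohort 2 but tested in the combined sample, and the plan does not say which contrast or coding answers it

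*Combined protocol and SAP*

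**What the plan says.** Section II states H1d as follows: "Participants assigned to receive CHW will demonstrate higher rates of biochemically-verified, 7-day point-prevalence tobacco abstinence than those assigned to TAU". The document treats CHW as an arm of its own. Section II speaks of "comparing AD+CHW, AD, CHW and TAU, we seek to achieve the following aims", and Section V says "This study aims to compare the effects of service interventions, AD+CHW, AD, CHW and TAU". The sentence on prescription fills in Section VII.2 lists the same four groups.

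On who was randomised to CHW without AD, Section III says: "Cohort 2 (AD-ineligible) comprised participants whose primary care clinic served ≤ 2 enrolled participants who were randomized to CHW or TAU". In Cohort 1, clinics were randomised to AD or TAU, and CHW was then randomised only among participants of AD clinics (Sections IV and V.3).

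On the test of H1d, Section VII.2 says: "This will be tested with factorial analysis in the combined sample, using cohort as a factor". Section VII.1 describes the same analysis: "we conducted a secondary, factorial analysis of the impact of the two interventions and their combination, using cohort as a factor". Section VII.1 also remarks that the Cohort 2 comparison may be held apart from the main three-arm analysis.

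For H1b (AD+CHW versus AD), Section VII.2 says: "This rate will be compared between the two groups using logistic regression". H1a, by contrast, has a logistic mixed model with a random effect for clinic.

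**The concern.** CHW was randomised against two different backgrounds. In Cohort 2 the comparison is CHW versus TAU, without AD. In Cohort 1 it is AD+CHW versus AD, which is H1b. A factorial analysis of both cohorts can return the first contrast, or a mixture of the two, under the same label of CHW effect. The plan does not say which quantity answers H1d.

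The two contrasts need not agree. Section VII.3 admits: "We are unsure of the effect the academic detailing (AD) intervention alone will have on abstinence rates". The H1b contrast could therefore be large or close to zero. A mixture reported as H1d could be positive only because CHW helps on top of AD. It could also miss a real effect of CHW without AD. Someone deciding whether to offer CHW support where AD is not feasible, which is the Cohort 2 situation, would read H1d as the answer.

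A smaller matter sits beside this. CHW was randomised within AD clinics, yet H1b is analysed without the clinic effect that H1a has.

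**Working it through.** **Inputs.** Cohort 2 is 155 of 1165, or 13.3%, which matches the stated 13%. Cohort 1 is 1165 - 155 = 1010. Clinics are allocated one third to TAU and two thirds to AD, with CHW offered to half of the participants in AD clinics. Assuming participants divide as clinics do, each Cohort 1 arm has 1010/3 = 336.7, and each Cohort 2 arm has 155/2 = 77.5. Tables 1 and 2 give TAU 3-5%, AD 7-14% and AD+CHW 16-18%. The plan gives no CHW-alone rate and no power for H1d, so that rate is assumed below.

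**Check against the plan's own figures.** The AD versus AD+CHW power column is the H1b contrast. With 300 per arm (900/3), two-sided 5% and no clustering, the two-proportion formula gives .935, .666, .101, .984, .858 and .266. The plan states .94, .67, .10, .96, .87 and .26.

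**Weights.** Five cells exist: Cohort 1 TAU, AD and AD+CHW, then Cohort 2 TAU and CHW. With intercept, cohort, AD, CHW and AD×CHW the design has rank 5, so it is saturated. Inverting it gives the cell weights of the CHW coefficient.

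| Model | Weights (C1 TAU, AD, AD+CHW; C2 TAU, CHW) | H1b share |
|---|---|---|
| Interaction, reference coding | (0, 0, 0; -1, 1) | 0% |
| Interaction, effect coding | (0, -.5, .5; -.5, .5) | 50% |
| No interaction, linear | (0, -.81, .81; -.19, .19) | 81% |

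Adding cohort×CHW leaves the rank at 5, so a different CHW effect with AD cannot be told apart from a different CHW effect between cohorts.

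**No interaction, logistic.** The CHW coefficient is approximately the information-weighted average of the two log odds ratios, where information = 1/[1/(n₁p₁(1-p₁)) + 1/(n₂p₂(1-p₂))]. With AD 7%, AD+CHW 16% and 5% in both Cohort 2 arms:

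- Cohort 1: 1/[1/(336.7×.0651) + 1/(336.7×.1344)] = 14.77
- Cohort 2: 1/[2/(77.5×.0475)] = 1.84
- H1b share: 14.77/16.61 = 89%

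Over all Table 1 and 2 rates, with CHW alone anywhere from the TAU rate to the AD+CHW rate, the share runs from 84% to 95%. The top is TAU and CHW alone 3%, AD 14%, AD+CHW 18%.

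**What this could do to H1d if CHW alone has no effect (5% vs 5%).** With AD 7% and AD+CHW 16%, the H1b log odds ratio is .93.

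- No interaction: .889×.93 = .83, a pooled odds ratio of 2.3 where the CHW-alone odds ratio is 1. At 79% retention the SE is 1/√(16.61×.79) = .276, so H1d is rejected about 85% of the time. A simulation with clinic random effects gave 88% and an odds ratio of 2.4. With AD at 9.5% the simulated figures are 62% and 1.8.
- Effect coding: half of .93 is .46, with SE ½√(1/11.66 + 1/1.45) = .44, so rejection is about 18%.
- Reference coding: this is the Cohort 2 contrast, and a score test on it rejects about 5%.

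**Precision of Cohort 2 alone.** Loss of 10-12% per year leaves 60-63 per arm. Exact enumeration of the score test for 5% versus an assumed 14-16% gives power of 40-54%. It is 49-64% if all 155 count (77-78 per arm).

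**H1b.** Simulations used 27 AD clinics (Section III expects 26-30), 673 participants, 79% retention and 9.5% versus 16%. With a clinic logit SD of .67, power was 61-63% for plain logistic regression and 63-64% for the mixed model. With an SD of 1.0 it was 61-62% and 65%. Under the null the plain test rejected 3.9-4.5%, against about 5% for the mixed model.

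**The case against.** Section VII.1 does name the ingredients: AD, CHW, their combination and cohort. That describes an interaction model, and such a model is saturated, so CHW versus TAU is the same estimable contrast under any coding. An analyst who tests H1d as worded gets the Cohort 2 comparison with no H1b in it. The 50% figure arises only if an effect-coded coefficient is read as H1d, and the 81-95% figures only if the interaction is dropped. Nothing in the document mentions effect coding or dropping the interaction. This argument stands as far as it goes. A reader might infer that the plan specifies no model, or that H1d is mostly H1b as planned, and the text supports neither. What remains is that the contrast and coding are not stated, and that announcing a combined-sample test suggests Cohort 1 is meant to contribute to the answer.

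A second argument is that pooling may be the better analysis. If CHW has the same odds ratio with and without AD and in both cohorts, the pooled estimate is valid and far more powerful. In simulation with CHW alone at 11.8% (odds ratio 2.53, AD 7%, AD+CHW 16%), the model without interaction had 95% power against 26% for Cohort 2. With AD at 9.5% and CHW alone at 8.7%, it was 70% against 13%. This stands as a reason to keep the pooled estimate. It does not remove the need to label it, because the data can hardly check the assumption. With TAU 5% and AD+CHW 16%, the SE of the difference between the two log odds ratios is at least .64, so 80% power needs a ratio of odds ratios near exp(2.80×.644) = 6.1.

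Finally, the factorial analysis is secondary, and Section VII.1 already allows a separate Cohort 2 comparison. Both points are correct and limit the weight of the concern.

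**Conclusion.** The point holds as a minor lack of specification. H1d as worded is randomised only in Cohort 2, the test uses both cohorts, and the contrast that answers it is not stated. On the natural interaction reading, 0% or 50% of the CHW term is the H1b contrast, depending on coding. These two figures are exact. On the less supported reading without interaction, the share is about 81% (linear) or 84-95% (logistic). Those figures rest on equal Cohort 1 arms, and the logistic range also on the Table 1 and 2 rates and an assumed CHW-alone rate.

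It would go too far to infer that the Cohort 2 estimate should replace the combined analysis. That is a trade of bias against precision, and the documents do not settle it. Nor is the H1b test invalid: plain logistic regression is slightly conservative here and costs about 1-4 points of power. H1a is unaffected and H1b is exploratory.

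**What to change.** 1. State that H1d is the simple CHW versus TAU contrast, and report the randomised Cohort 2 estimate with its confidence interval. Show any combined-sample CHW estimate beside it, with its model terms and coding. Label it as assuming an equal CHW effect with and without AD and across cohorts. If it comes from a model without interaction, say that it is drawn mostly from AD clinics in Cohort 1.
2. Analyse H1b with the same clinic random-effect logistic model as H1a.

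The cost is one extra estimate from data already collected, a label, and one model term. The drawback is imprecision: the Cohort 2 interval will be wide, which is why the combined estimate should stay. Section VII.1 describes the factorial analysis as already carried out, so the Cohort 2 result should be added and marked as a clarification, without withdrawing the combined one.

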their primary care team in the past year. Study staff will attend the IAP meeting for those who agree. Study staff will follow a brief script to explain the study to participants, to inform them that participation in the 3 brief annual surveys is entirely voluntary, that their decision of whether or not to participate will in no way impact their ongoing psychiatric rehabilitation services or primary care, and to obtain verbal consent from those who agree to answer the smoking and smoking-treatment-related questions. Participants will be asked to complete the survey on 3 occasions, on an annual basis, once before clinic randomization (Year One, baseline) and twice after the intervention has been implemented (Years 2 and 3). We expect 85-90% of potential participants (n=900) to agree to participate in this 5-minute survey once a year for 3 years at their annual IAP meeting or other setting in which they interact with their psychiatric rehabilitation team members. Those who complete the survey will be reimbursed \$5 for their time. Study staff who administer the survey will be trained in the process for obtaining verbal consent, in privacy standards such as the HIPAA privacy rule, and in adherence to the study protocol, including data collection methods.

Procedures protecting confidentiality.

Staff employed at the human service agencies providing psychiatric rehabilitation services (Bay Cove Human Services and Vinfen) will create a database that assigns a study identification number (random numeric value) to each of their clients that they have identified as a smoker. The names of eligible participants under their care and the key linking these names to study IDs will be available only to the psychiatric rehabilitation agency staff. MGH staff who administer the surveys in Years 1-3 will have access only to study IDs and, at the time of the survey, to first names of participants. MGH study staff will identify surveys with study IDs only.

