In order to examine the effect of the study interventions on rates of prescribing smoking cessation medication (i.e. varenicline, bupropion and nicotine replacement therapy) we will receive deidentified MassHealth pharmacy claims data for all study participants who are covered by MassHealth. To maintain the firewall between the human services agencies (Bay Cove and Vinfen) and MGH, we will use a multi-step process to obtain deidentified claims data from MassHealth. First, the human services agencies will send MassHealth a file that contains participants' Study IDs linked with MassHealth ID. Next, MGH will send MassHealth a file with participants' Study IDs linked with a limited set of patient study data including, study arm, dates of Year 1 (baseline), Year 2 (intervention year 1), and Year 3 (intervention year 2) data collection, age group (in ten year increments), gender, race (White, Black, Asian, Other), ethnicity (Hispanic, Not Hispanic), self-reported smoking cessation medication use (varenicline, bupropion, nicotine replacement therapy) at Year 1 (baseline), Year 2 (intervention year 1), and Year 3 (intervention year 2), and self reported abstinence at baseline, year 1 and year 2.

MassHealth will link prescription fill data for smoking cessation medications (January 2015-June 2020) with the limited set of patient study data, but strip all study and the MassHealth IDs before returning the data to MGH. Specifically, MassHealth will create a new encrypted ID for each participant only, which will not be linkable with the main study IDs, thus deidentifying the data we receive and analyze. MassHealth will also replace medication fill dates with flags corresponding to which of the study year windows the medication was filled (year prior to

baseline, baseline-interventionY1, intervention Y1-Y2) and strip exact dates from the file. Thus, we will receive a deidentified file from MassHealth that contains the following information:

Encrypted ID
Coverage indicators (e.g., dual-eligibility, MassHealth plan type (e.g., MCO, FFS))
Death Flag (Y/N) during Post-intervention period
Claims for smoking cessation medications (i.e., varenicline, bupropion, NRT)
Indicator for fill date during either pre vs. post intervention window
National Drug Code (NDC)
Drug generic/brand name
Quantity filled
Days supply
New or refill indicator
Drug costs (e.g., Medicaid paid amount, Patient paid amount (i.e. co-pay))
Claim version / Claim denial flag
Prescribing provider

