Exploratory Aim 3: Through data collected by the RAs for both AD+CHW and TAU groups, we will identify differences in care processes that will be suggestive of specific mechanisms. The main components of the intervention are i) AD to prescribers, which is designed to increase the number of smoking cessation interventions initiated including prescriptions written and referrals for behavioral treatment; and ii) the availability of CHW

support to patients and providers, which is intended to improve client engagement with prescriber recommended tobacco treatment, including increasing access to, and use of tobacco treatment pharmacotherapies and attendance at behavioral smoking cessation treatment. The CHW, through encouraging cessation attempts and through client support, is expected to increase the effectiveness of the pharmacotherapies and behavioral groups, and reduce relapse risk. We will conduct exploratory analyses examining differences in self reported prescriptions received, prescriptions filled, and smoking cessation groups attended by study arm using linear mixed effects models with clinic random effects.

Exploratory Aim 4. Hypothesis 4a: *Participants with schizophrenia and schizoaffective diagnoses will demonstrate lower absolute rates of biochemically-verified, 7-day point-prevalence tobacco abstinence than those with other diagnoses.* This rate will be compared between the two groups using generalized linear mixed models logistic regression.

Hypothesis 4b. *Participants with schizophrenia and schizoaffective diagnoses will a demonstrate larger effect of treatment (AD+CHW) vs no treatment (TAU).* This effect will be compared between the two groups using generalized linear mixed models logistic regression. These hypotheses are underpowered to detect an effect and are considered to be exploratory only.

Aim 5: We will use an interactive convergent design, as the emerging qualitative and quantitative data findings will inform respectively additional analyses. Our interactive intramethod approach or “iterative approach” will allow for us to generate hypotheses resulting from the qualitative data analysis which we will examine quantitatively using Year 3 data to further inform the joint display analysis.

Quantitative Data Analysis

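### The process-of-care comparisons leave out each outcome's own pre-randomisation value, which costs precision but causes no bias, and advice to quit, named in Aim 1, has no planned analysis

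*Combined protocol and SAP*

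**What the plan says.** Aim 1 (section II) asks whether AD+CHW "increases prescriber provision of advice and assistance to quit smoking and improves tobacco abstinence rates in smokers with SMI". Hypotheses 1a to 1d, which follow from it, all concern abstinence.

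Section IV gives the survey "once before clinic randomization (Year One, baseline) and twice after the intervention has been implemented (Years 2 and 3". Item 2.3 (section V, Survey Items) covers past-year cessation services from primary care, including "whether advice to quit smoking was given", prescriptions, referrals, fills and use. The Time and Events Table schedules the smoking questionnaire in all three years.

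For the MassHealth file, section IV lists an "Indicator for fill date during either pre vs. post intervention window". The text before the list says fill dates become window flags, one of which is the year before baseline.

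Section VII.2 plans two sets of process analyses:

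- **Claims, under Aim 1.** Claims are compared "to examine differences in prescribing patterns of providers randomized to AD compared to those randomized to TAU", followed by: "We will also examine the effect of the interventions on rates of participants filling prescriptions for smoking cessation medication". No model and no pre-period term is named.
- **Survey, under Exploratory Aim 3.** The outcomes are self-reported prescriptions received, "prescriptions filled, and smoking cessation groups attended by study arm using linear mixed effects models with clinic random effects". No baseline term is named.

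In the same section, the Aim 2 model for the SF-1 does list baseline as a covariate.

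**The concern.** These outcomes show whether academic detailing changed what prescribers did and whether patients took it up. Clinics are likely to differ in prescribing habits before any intervention, and section III expects only 13 to 15 TAU clinics. With so few, the arms can differ by chance in prior prescribing. A model with arm and a clinic random effect carries that variation in its standard error but does not use the pre-randomisation measurement to remove any of it. Aim 2 shows that the authors adjust for baseline elsewhere.

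The second matter is one of coverage. Aim 1 names advice first, and the survey collects it, but section VII contains no outcome, hypothesis or model for it. A change in advice-giving could be reported in any way after the data are seen, or not at all.

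**Working it through.** **1. The plan's own figure.** The documents give no power or precision for any process outcome. The nearest figure is Table 1, row 1 (section VII.3): abstinence of 5% (TAU) vs 16% (AD+CHW), ICC 0.03, power 0.96. It serves only to check the cluster inputs.

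- Inputs: 900 patients and 40 clinics (section VII.4), so 900/40 = 22.5 per clinic. One third of clinics are TAU, and AD patients are split 1:1, so about 300 patients per arm and 22.5/2 = 11.25 AD+CHW patients per AD clinic.
- Design effects: TAU 1 + 21.5 × 0.03 = 1.645; AD+CHW 1 + 10.25 × 0.03 = 1.3075.
- Two-proportion power with 300/1.645 and 300/1.3075 patients (two-sided 5% level assumed) is 0.953. A 1000-run simulation with a cluster-robust test gives 0.952. Both agree with 0.96.
- Over all 18 cells of Tables 1 and 2, the formula is within 2 points in 12. The misses are mostly TAU vs AD (for example 0.51 stated, 0.40 computed). Nothing below depends on those cells.

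**2. Gain from baseline adjustment.** For a contrast between clinics, adjusting for the participant's baseline value and its clinic mean multiplies the variance by about 1 − r², where

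r = [mρπ + (1 − ρ)τ] / [1 + (m − 1)ρ].

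Here m is patients per clinic, ρ the ICC, π the clinic-level and τ the individual-level year-to-year correlation. The documents give neither π nor τ, so 0.6-0.8 and 0.2-0.4 are assumptions. The ICC of 0.03 is the plan's figure for abstinence, carried over to the process outcomes.

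| m | ρ | π | τ | r | SE factor |
|---|---|---|---|---|---|
| 20 | 0.03 | 0.6 | 0.2 | (0.36 + 0.194)/1.57 = 0.353 | √(1 − 0.125) = 0.94 |
| 20 | 0.03 | 0.8 | 0.4 | (0.48 + 0.388)/1.57 = 0.553 | √(1 − 0.306) = 0.83 |
| 10 | 0.03 | 0.6 | 0.2 | (0.18 + 0.194)/1.27 = 0.294 | 0.96 |
| 10 | 0.03 | 0.8 | 0.4 | (0.24 + 0.388)/1.27 = 0.494 | 0.87 |
| 20 | 0.03 | 0.3 | 0.1 | (0.18 + 0.097)/1.57 = 0.176 | 0.98 |

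At 20 per clinic the standard error falls by about 6% to 17%. At 10 per clinic, close to the AD+CHW share of an AD clinic, it falls by 4% to 13%. With weak correlations (last row) it falls by about 2%.

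**3. What this could mean for power.** Take assumed process rates of 20% vs 30% with the clusters and ICC of step 1. Unadjusted power is 0.64. It becomes 0.68 at r = 0.3, 0.77 at r = 0.5 and 0.83 at r = 0.6. At r = 0 nothing is gained.

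**4. Where the formula does not apply.**

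- AD+CHW vs AD is randomised within clinics and Cohort 2 is individually randomised. The gain there comes almost wholly from τ: √(1 − 0.04) = 0.98 to √(1 − 0.16) = 0.92, or 2% to 8%.
- The listed claims fields (section IV) include the prescribing provider but no clinic identifier, so the clinic-level gain does not carry over to claims.

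**5. Coverage of Aim 1.**

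| Component of Aim 1 | Collected | Analysed in section VII |
|---|---|---|
| Advice to quit | Item 2.3 | No |
| Assistance | Item 2.3; claims | Yes: self-reported prescriptions and fills; claims prescribing and fills |
| Abstinence | Survey with CO and cotinine | Yes: Hypotheses 1a-1d |

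**6. Who answers item 2.3.** It is put to those who are smoking. Enrolees are smokers, so Year 1 values should exist. At follow-up, participants who have quit may have none, and section VII.3 expects abstinence of 3-5% under TAU and 16-18% under AD+CHW. The group with data would therefore be selected by an outcome that differs between arms.

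**The case against.** Exploratory Aim 3 gets a one-sentence model description, and silence on baseline is not a decision to exclude it. Requesting pre-period claims suggests that they were meant to be used. This has some force for the claims comparisons, where no model is given. It has less for the survey outcomes, where the plan does state a model, and the Aim 2 model in the same section shows how a baseline term is written when intended.

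A reader might infer that the comparison is biased by prior differences between clinics. The documents do not support that: clinics were randomised, and the clinic random effect carries chance imbalance into the standard error. The cost is precision only.

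A reader might also infer that Aim 1, or its whole provider half, goes untested. It does not. Claims prescribing and fills are compared under Aim 1, prescriptions and fills again under Exploratory Aim 3, and section IV says in general terms that provision of treatment will be analysed. Only advice is missing.

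It is also fair to say that the size of the gain rests on assumed correlations and that the self-report analyses are labelled exploratory. Both stand. They limit how much the point matters but give no reason to leave the baseline out.

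**Conclusion.** The point holds as a matter of efficiency and of one missing outcome. The stated survey model uses no Year 1 value and the claims comparisons name no pre-baseline term, although both kinds of data predate randomisation. For clinic-randomised contrasts of the survey outcomes, adjustment would reduce the standard error by about 6% to 17%, given 20 patients per clinic, ICC 0.03 and the assumed correlations. Low correlations would make the gain small.

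Larger figures are tempting. An ICC of 0.10 with the higher correlations gives r = (1.6 + 0.36)/2.9 = 0.676 and a 26% reduction. The documents use 3%, and 7% as a sensitivity value, both for abstinence; they never use 0.10.

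Advice to quit is the only part of Aim 1 without an analysis. Adding it is worthwhile only if the handling of participants who have quit is settled, since restricting to continuing smokers conditions on a post-randomisation outcome. Baseline adjustment does not repair that, and the same caution applies to the survey process outcomes already planned.

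**What to change.** - **Section VII.2, Exploratory Aim 3:** add the participant's Year 1 value of the same item, and its clinic mean, as covariates in each process model.
- **Section VII.2, claims comparisons under Aim 1:** name the model and add a person-level indicator of any fill in the year before baseline.
- **Section VII.2, Aim 1:** name advice to quit as an outcome, AD+CHW vs TAU, using a logistic mixed model with a clinic random effect and the Year 1 value as covariate. State whether item 2.3 was put to participants who had quit. If it was not, state how they enter the analysis and add a sensitivity analysis for their missing values.

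The baseline changes cost only analysis-plan wording and need no new data. The advice analysis also needs none if quitters were asked; otherwise it needs an explicit missing-data assumption. Section VII.1 describes some analyses in the past tense. If the process analyses have already been run, report the adjusted results and the advice outcome as additions beside the planned ones.
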